#### ***9.5.2.8 Return to Continence***

An analysis of return to continence post RALRP will be performed using the pad weight test. Patients will be classified as being continent if the weight of the pad increase is insignificant; mild incontinence if the weight of pad increases by <400 grams over 24 hours and as incontinent if the weight of the pad increases by  $\geq 400$  grams over 24 hours. The pad weight test will be performed at the following post-RALRP timepoints: 12 days (if urinary catheter is removed), 3 months, 6 months, 9 months, and 12 months. The proportion of continent patients will be calculated for each treatment group at each timepoint. Treatments will be compared using an exact binomial sign test.

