### **2.2 Secondary Objectives**

The key secondary objectives are to assess the outcomes listed below and to compare the results for patients who receive PAE and those that do not:

1. Change in hemoglobin on RALRP post operative day (POD) 1 compared to baseline
2. Change in hematocrit on RALRP post operative day (POD) 1 compared to baseline
3. Change in prostate volume between baseline and Visit 3 (6 weeks  $\pm$  2 weeks post PAE) as determined by MRI in patients who receive PAE
4. Blood transfusion requirements during RALRP
5. RALRP duration in minutes
6. Length of hospital stay for RALRP
7. Presence or absence of a complete surgical margin around the entire tumor as determined by histopathology examination post RALRP
8. Biochemical recurrence of prostate cancer as determined by PSA levels post RALRP at 1 year follow up
9. Return to continence post RALRP as assessed by the pad weight test.
10. RALRP related adverse events
11. Erectile function compared to baseline as assessed by the IIEF post RALRP at 1 year follow up.

Additional secondary objectives are to assess outcomes listed below for patients that receive PAE:

12. Change in PSA between baseline and Visit 3 (6 weeks  $\pm$  2 weeks post PAE)
13. PAE related adverse events
14. Histologic changes in the prostate after PAE

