### **3 PAE Patient Population**

#### **3.1 Inclusion Criteria**

Patients must meet all of the following inclusion criteria in order to be entered into the study:

1. Patient is 45-79 years old
2. Patient has signed informed consent
3. Patient must have biopsy-proven prostate adenocarcinoma with localized disease
4. Patient must be a candidate for robot-assisted radical prostatectomy (RALRP)
5. Patient has a prostate size >40 grams

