### 3.2 Exclusion Criteria

Patients meeting any of the following exclusion criteria may not be entered into the study:

1. Active urinary tract infection
2. History of life threatening allergy to iodinated contrast agents
3. Any known condition that limits catheter-based intervention or is a contraindication to embolization (eg shunt or adverse arterial anatomy)
4. Patient is unable to undergo MRI imaging
5. Cardiac condition including congestive heart failure or uncontrolled arrhythmia, uncontrolled diabetes mellitus, significant respiratory disease, or known immunosuppression which required hospitalization within the previous 6 months.
6. Baseline serum creatinine level  $> 1.8$  mg/dL
7. Baseline hemoglobin  $< 8.0$  g/dL
8. Active cystolithiasis or prostatitis
9. History of pelvic irradiation or radical pelvic surgery
10. Known major iliac arterial occlusive disease
11. Confirmed or suspected bladder cancer
12. Urethral strictures, bladder neck contracture, or other bladder or urethral pathology that could limit catheterization
13. Previous rectal surgery (other than hemorrhoidectomy) or history of rectal disease if the therapy or patient evaluation may potentially cause injury to sites of previous rectal surgery, e.g. if a transrectal probe is used
14. Previous pelvic irradiation or radical pelvic surgery
15. Previous prostate surgery, balloon dilatation, stent implantation, laser prostatectomy, hyperthermia, or any other invasive treatment to the prostate
16. Prior transurethral resection of the prostate or other invasive therapies
17. Coagulation disturbances not normalized by medical treatment
18. Acute urinary retention
19. Hypersensitivity to gelatin products
20. Any contraindication to embolization, including intolerance to vessel occlusion procedures, vascular anatomy/blood flow that precludes catheter placement or embolic agent injection, presence/likely onset of vasospasm, presence/likely onset of hemorrhage, severe atheromatous disease, feeding arteries smaller than distal branches, arteriovenous shunt, and collateral vessel pathways endangering normal territories during embolization or pelvic inflammatory disease

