### 4.2 Control Patients

A similar cohort of patients who undergo RALRP without PAE will be treated as a matched control group. The controls will be matched using a 1:1 ratio to PAE treated patients based on AUA risk group. Risk stratification will be as follows, according to AUA guidelines:

- Low risk: Stage T1c to T2a tumors, AND PSA  $\leq 10$ ng/mL, AND Gleason score  $\leq 6$

- Intermediate risk: Stage T2b tumors, OR PSA > 10ng/mL but ≤ 20ng/mL, OR Gleason score 7
- High risk: Stage T2c or higher tumors, OR PSA > 20ng/mL, OR Gleason score 8-10

Control patients will be selected after 10 patients for the PAE arm have been identified, such that the first potential control patient who matches the risk score of a PAE patient and agrees to participate in the study is matched to the appropriate member of the PAE arm. Once a match is identified, additional matches for a single PAE patient will not be sought. Because we are matching PAE and control patients based on AUA risk score only, we do not anticipate difficulty in finding a matched control for every PAE patient.

Control patients will sign written informed consent before any study-specific assessments are performed. Patients will complete EPIC and IIEF questionnaires within 12 weeks prior to RALRP, and will undergo MRI as a baseline study. Oncologic and functional outcomes will be evaluated by assessing PSA, EPIC, and IIEF at months 3, 6, 9, and 12 post RALRP, and then annually per standard follow-up protocol for the treating institution.

Safety will be evaluated for PAE patients throughout the study treatment and assessment periods by assessing adverse events, concomitant medications, changes in laboratory values, and findings on physical examination. Safety will be evaluated for Control patients during RALRP and the follow up period by assessing adverse events and concomitant medications.

The patients in both groups will continue to be followed post RALRP according to standard follow up protocol for the treating institution.

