### **5.6 Visit 5 (12 days +/- 7 days)**

Patients in the PAE group and the Control group will have the following:

- Physical exam including vital signs, weight, and genitourinary evaluation
- Blood and urine laboratory evaluations as at baseline
- Concomitant medications
- Adverse events
- Urinary catheter removal

Cystoscopy and proctoscopy will be performed: 1) if medically indicated, especially if there is pain out of proportion to that which is expected, 2) in all cases of bleeding per rectum, and 3) in cases of hematuria beyond that which is reasonably expected following prostatectomy.**5.7 Visits 6, 7, 8, 9 (3, 6, 9, and 12 months ± 2 weeks for each visit post RALRP)**

Patients in the PAE group will have the following assessments performed:

- Physical exam including vital signs, weight, and genitourinary evaluation
- Prostate Specific Antigen (PSA)
- Expanded Prostate Cancer Index Composite (EPIC) questionnaire
- International Index of Erectile Function (IIEF) questionnaire
- Pad weight test
- Concomitant medications
- Adverse events

Cystoscopy and proctoscopy will be performed: 1) if medically indicated, especially if there is pain out of proportion to that which is expected, 2) in all cases of bleeding per rectum, and 3) in cases of hematuria beyond that which is reasonably expected following prostatectomy.

Patients in the Control group will have the following assessments performed:

- Physical exam including vital signs, weight, and genitourinary evaluation
- Prostate Specific Antigen (PSA)
- Expanded Prostate Cancer Index Composite (EPIC) questionnaire
- International Index of Erectile Function (IIEF) questionnaire
- Pad weight test
- Concomitant medications
- Adverse events

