## Appendix D: Expanded Prostate Cancer Index Composite

URINARY FUNCTION							
		More than once a day	About once a day	More than once a week	About once a week	Rarely or never	YOUR SCORE
1.	Over the past 4 weeks, how often have you leaked urine?	1	2	3	4	5	
2.	Over the past 4 weeks, how often have you urinated blood?	1	2	3	4	5	
3.	Over the past 4 weeks, how often have you had pain or burning with urination?	1	2	3	4	5	
		No urinary control whatsoever	Frequent dribbling	Occasional dribbling	Total control		YOUR SCORE
4.	Which of the following best describes your urinary control during the last 4 weeks?	1	2	3	4		
		None	1 pad per day	2 pads per day	3 or more pads per day		YOUR SCORE
5.	How many pads or adult diapers per day did you usually use to control leakage during the last 4 weeks?	0	1	2	3		
		No problem	Very small problem	Small problem	Moderate problem	Big problem	YOUR SCORE
6.	How big a problem, if any, has each of the following been for you during the last 4 weeks?						
	a. Dripping or leaking urine	0	1	2	3	4	
	b. Pain or burning on urination	0	1	2	3	4	
	c. Bleeding with urination	0	1	2	3s	4	
	d. Weak urine stream or incomplete emptying	0	1	2	3	4	
	e. Waking up to urinate	0	1	2	3	4	

	f. Need to urinate frequently during the day	0	1	2	3	4	
		No problem	Very small problem	Small problem	Moderate problem	Big problem	YOUR SCORE
7.	Overall, how big a problem has your urinary function been for you during the last 4 weeks?	1	2	3	4	5	

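### Return to continence is judged from post-operative pad weight alone, with nothing in the plan establishing that a man was continent before treatment

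*Combined protocol and SAP*

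**What the plan says.** Key secondary objective 9 in section 2.2 is "Return to continence post RALRP as assessed by the pad weight test", compared between patients who receive PAE and those who do not.

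The analysis is in section 9.5.2.8. On timing it says "The pad weight test will be performed at the following post-RALRP timepoints: 12 days (if urinary catheter is removed), 3 months, 6 months", and the list goes on to 9 and 12 months. Each man is classified by the pad-weight increase at that timepoint. The proportion continent is reported per arm and timepoint, and the arms are compared with an exact binomial sign test. There is no baseline term, change from baseline or restriction to men continent beforehand.

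Elsewhere in the same document:

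- **Eligibility (3.1, 3.2).** None of the five inclusion or twenty exclusion criteria concerns continence. The closest are urinary conditions such as "Acute urinary retention". Section 4.2 sets no continence requirement for controls.
- **Matching (4.2).** "Because we are matching PAE and control patients based on AUA risk score only", so urinary function is not a matching factor.
- **Baseline visit (5.1, Appendices A1 and A2).** No pad test in either arm. EPIC is completed in both arms.
- **Follow-up (5.7, Appendices A1 and A2).** The pad test appears only at Visits 6 to 9, "3, 6, 9, and 12 months ± 2 weeks for each visit post RALRP".
- **Visit 5 (5.6).** The list includes "Urinary catheter removal" but no pad test.
- **EPIC (Appendix D).** Item 1 asks about leakage, item 4 about urinary control, and item 5 begins "How many pads or adult diapers". Section 9 contains no analysis of EPIC.

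**The concern.** A man can return to continence only if he had it before. As written, the endpoint is post-operative continence status under the label of return. Two different men are counted alike: one who lost continence through surgery and has not recovered it, and one who leaked before any study procedure and still does.

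In a randomized trial, allocation would balance the second kind in expectation. Here, PAE patients are enrolled consecutively and each control is the first consenting man in the right AUA risk group. Neither step balances prior leakage, so any arm difference in persistent pre-existing leakage enters the comparison as if it were an effect of PAE.

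The parallel functional outcome is handled differently. Section 9.5.2.9 defines a baseline for erectile function (pre-PAE in one arm, pre-RALRP in the other) and analyses change from it. Section 9.1 says the PAE group's baseline is specified outcome by outcome; for continence it is not.

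**Working it through.** The plan gives no sample-size, power or alpha figure for this endpoint, so there is no stated number to reproduce. The check has four parts.

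**1. What makes a man a failure.** Two definitions stand side by side:

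| Pad-weight increase over 24 h | Section 8.3 | Section 9.5.2.8 |
|---|---|---|
| insignificant (no value given) | continent | continent |
| below 400 g | continent | mild incontinence |
| 400 g or more | incontinent | incontinent |

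Under 8.3, only persistent leakage of at least 400 g counts as failure. Under 9.5.2.8, much smaller leakage takes a man out of the continent group. Under both, the leakage must be present at the post-operative visit; leakage that has resolved does no harm.

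**2. Effect of one man.** With 10 men per arm (section 9.2), one man is 1/10 = 10 percentage points of his arm's proportion.

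**3. Effect on the sign test.** No significance level is stated; two-sided 0.05 is assumed for illustration. With m discordant pairs all in one direction, p = 2 × 0.5^m:

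- m = 5: 2/32 = 0.0625
- m = 6: 2/64 = 0.031

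So at least 6 one-way discordant pairs out of at most 10 are needed. One man whose status changes moves his pair between concordant and discordant. He cannot by himself turn a pair from favouring one arm to favouring the other. Starting from 6 of 6 in favour of PAE (p = 0.031), one PAE man counted as not continent because of old leakage can:

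- remove a favourable pair, giving 5 of 5, p = 0.0625; or
- turn a both-continent pair against PAE, giving 6 of 7, p = 2 × (7 + 1)/128 = 0.125.

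A control man with old leakage works the other way and can lift 5 of 5 (0.0625) to 6 of 6 (0.031).

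**4. Chance of an arm difference.** The documents give no rate of baseline leakage, so a rate r is assumed, equal in both arms. With b(x) = C(10, x) r^x (1 − r)^(10 − x), the probability that the arms differ by at least one such man is 1 − Σ b(x)².

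- r = 5%: b(0) to b(3) are 0.5987, 0.3151, 0.0746, 0.0105; squares sum to about 0.46; result 0.54.
- r = 10%: b(0) to b(4) are 0.3487, 0.3874, 0.1937, 0.0574, 0.0112; squares sum to about 0.31; result 0.69.

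| Assumed r | At least one of 20 men, 1 − (1 − r)^20 | Arms differ by at least one |
|---|---|---|
| 2% | 0.33 | 0.30 |
| 5% | 0.64 | 0.54 |
| 10% | 0.88 | 0.69 |
| 20% | 0.99 | 0.78 |

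The last column is the relevant one, and it is still an upper reading, because it treats every man with baseline leakage as a later failure. If, say, half of a 10% group still leaked above the cutoff, the effective rate would be 10% × 0.5 = 5% and the figure 0.54 rather than 0.69.

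**12-day timepoint.** Section 9.5.2.8 analyses a pad test at 12 days. Section 5.6 and the pad-test rows of Appendices A1 and A2 have none at Visit 5. Section 8.3 requires 24 hours of wear, and the catheter is removed at that same visit.

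**The case against.** The best defence is that the plan does what objective 9 asks. Objective 11 (erectile function) is explicitly set against baseline; objective 9 is not, and names the pad weight test as its measure. Post-operative status fits that text, and the criticism leans on one word. This has some force, and it is why the all-patient comparison should stay. It does not answer the confounding: a status comparison between non-randomized arms still needs baseline status to be interpretable.

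A second defence is that prior leakage is not invisible. EPIC, medical history, concurrent conditions and a genitourinary examination are recorded at Visit -1 in both arms, and section 9.1 promises listings of all CRF data. With 20 men, an affected patient could be found by eye. That is right, and a reader who inferred that baseline continence goes unrecorded would be wrong. What is missing is a prespecified definition and its link to the endpoint.

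Third, a reader might infer that any pre-existing leakage becomes a post-operative failure, or that the 64% and 88% chances of enrolling at least one such man are chances of a wrong result. The documents support neither: failure requires persistence and a cutoff on which they disagree, and bias requires a difference between arms.

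Fourth, restricting the analysis to men continent at baseline breaks pairs, and there are at most 10. This stands, so the restricted analysis should accompany the full one, not replace it.

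**Conclusion.** The concern holds in limited form. Section 9.5.2.8 labels as return an endpoint that uses no information on prior continence, and the design does not balance that factor between arms. Each man with persistent pre-existing leakage above the cutoff shifts his arm by 10 points, and one such man can carry the sign test across 0.05 when the count of discordant pairs is near the minimum of 6. How likely this is cannot be derived from the documents. The 54% and 69% rest on assumed, equal leakage rates of 5% and 10% and on independence between men, and they overstate misclassification. A systematic arm difference would add to chance imbalance.

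The cutoff conflict between 8.3 and 9.5.2.8 affects every patient and comes first, since until it is settled the size of this problem is undefined.

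The 12-day mismatch is a separate inconsistency. A reader might conclude that the 12-day comparison cannot be produced. That goes too far, since 9.5.2.8 itself calls for the test, but no visit list or schedule tells the site to do it.

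Priority is low: this is one of many secondary outcomes in a proof-of-concept study without formal sizing. The correction is cheap.

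**What to change.** 1. **Reconcile the cutoff.** Make sections 8.3 and 9.5.2.8 give one definition, with a value for what counts as insignificant.
2. **Define baseline continence in 9.5.2.8** from the Visit -1 EPIC, pre-PAE in the PAE arm and pre-RALRP in controls. Name the visit: PAE patients also complete EPIC at Visit 3, and the closest-value rule in section 9.1 could otherwise select a post-PAE answer. Use items 1, 4 and 5 and state the response required on each. Zero pads on item 5 alone is not enough, because a man can leak or dribble without using pads.
3. **Tabulate baseline continence by arm.**
4. **Report the comparison twice:** for all pairs, as post-operative continence status; and for pairs in which both men were continent at baseline, as return to continence.
5. **Align the 12-day timepoint.** Either delete it from 9.5.2.8, or add the pad test to section 5.6 and Appendices A1 and A2, allowing for 24 hours of wear after catheter removal.

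Items 1 to 4 are wording changes that use data already planned. Their price is possibly one or two fewer pairs in the restricted analysis, and a baseline from self-report set against a weighed outcome. For item 5, deletion is wording only; adding the test is a schedule amendment with new data collection.

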The enhanced dissection capabilities of robotic surgery have the potential to mitigate the increased morbidity associated with operating on large prostate sizes (22). At present however, the technical challenges of operating on large prostates are compounded by poor visualization (22,23,27). Preoperative therapies that reduce prostate size may thus improve intraoperative visualization and consequently lead to reduced procedure times, decreased blood loss, and expedite return to continence and sexual function.

Androgen deprivation therapy (ADT) has been used to reduce prostate size prior to surgery and radiation treatment (28-32). ADT typically requires at least 3 months to achieve a reduction in

prostate size. However, there are significant side effects of treatment including bone and chest pain, rapid weight gain, cough, frequent/painful urination, headache, vision problems, depression and hormonal symptoms such as hot flashes, gynecomastia, testicular atrophy and impotence (28-32).

Although they allow better visualization and mobility, smaller prostates present challenges of their own. Numerous studies have reported statistically significant higher incidences of positive surgical margins in prostates smaller than 50g (22, 25, 33). Improving intraoperative visibility by reducing blood loss during RALRP may have a positive impact on surgical margin status for smaller prostate sizes.

In this study, we explore a new methodology for volumetric reduction of prostate along with concomitant reduction of vascularity of the prostate gland. Our hypothesis is that the prostate volumetric reduction along with reduced gland vascularity will result in a reduction of blood loss and improved visualization translating into superior surgical outcomes with regard to both short-term morbidity and long-term oncologic and functional outcomes.

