## **6 Withdrawal of Patients**

Patients will be informed that they have the right to withdraw from the study at any time for any reason, without prejudice to their medical care. The Investigator also has the right to withdraw patients from the study for any of the following reasons:

- Adverse events
- Refusal of treatment
- Patient request
- Inability to complete study procedures
- Lost to follow up
- Noncompliance with study requirements

If a patient is withdrawn or discontinued from the study, the reason for withdrawal from the study will be recorded in the source documents and on the Study Termination CRF. All patients withdrawn from the study will be encouraged to complete, if possible, all clinical evaluations scheduled for the 12 month visit. All adverse events should be followed as described in Section 7. Patients who are withdrawn from the study for any reason will not be replaced.

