### **8.3 Pad Weight Test**

Continence will be assessed using the pad weight test. Patients will wear a special pad designed to capture urine leakage for 24 hours. After 24 hours the pad will be weighed to evaluate the amount of urine collected. An increase of <400g indicates continence and an increase of  $\geq$ 400g indicates incontinence.

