### **9.2 Sample Size Calculations**

This is a proof of concept study and therefore, formal sample size calculations were not performed. Ten patients will be assigned in a non-randomized sequential manner to the PAE treatment group. Ten patients will also be assigned as matched controls in a 1:1 ratio to PAE treated patients based on risk group as defined in section 4.2. This sample size will provide sufficient data to assess the preliminary safety and efficacy of PAE treatment prior to RALRP.

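### Continence is weighed in grams but compared only as a proportion by a sign test on at most ten pairs; a paired comparison of the grams should be added.

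*Combined protocol and SAP*

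**What the plan says.** Section 8.3 (Pad Weight Test) describes a measured quantity: "After 24 hours the pad will be weighed to evaluate the amount of urine collected". It then cuts the scale in two at 400 g: "An increase of <400g indicates continence and an increase of" 400 g or more indicates incontinence.

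Section 9.5.2.8 (Return to Continence) uses three classes. "Patients will be classified as being continent if the weight of the pad increase is insignificant"; a gain below 400 g is mild incontinence, and 400 g or more is incontinence. No gram value is given for an insignificant increase. The comparison then uses one class only: "The proportion of continent patients will be calculated for each treatment group at each timepoint". The test is named in one sentence: "Treatments will be compared using an exact binomial sign test". The listed times are day 12 (if the catheter is out) and months 3, 6, 9 and 12.

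On numbers, Section 9.2 says: "Ten patients will also be assigned as matched controls in a 1:1 ratio to PAE treated patients", and Section 6 adds: "Patients who are withdrawn from the study for any reason will not be replaced". Ten pairs is therefore a ceiling. Section 9.2 gives no formal sample size, and no section states an alpha level or sidedness.

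Section 9.5.2.3 treats transfusion differently. It plans a sign test on yes/no and a second analysis of the amount by matched pairs t-test.

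**The concern.** Return to continence is secondary objective 9 in Section 2.2, and Section 1.2 hopes that reducing prostate size before surgery may "expedite return to continence and sexual function". The pad test yields a weight for each man at each visit, but the only planned comparison discards everything except which side of a boundary he falls on. The sign test then discards every pair in which both men fall on the same side. With ten pairs or fewer, little may be left to compare.

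Hemoglobin, hematocrit, operating time, length of stay and IIEF change are all compared on their measured scales, and transfusion is compared both ways. Continence is the measured outcome for which the plan states a cut and names no comparison of the quantity. What is at stake is sensitivity: a real fall in leakage could easily go undetected although the data that might show it are collected.

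**Working it through.** The plan gives no alpha, power or effect size, so it has no figure of its own to reproduce.

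**Inputs from the documents.** At most 10 pairs (9.2), withdrawals not replaced (6), exact sign test on the proportion continent (9.5.2.8), weight in grams (8.3).

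**Assumptions.** Two-sided 0.05 (one-sided also shown); continence rates of 40% v 80%, 50% v 80% and 80% v 95% (control v PAE); pairs uncorrelated; pad weight normal on a log-type scale with equal spread in both groups.

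**Step 1: what the sign test needs.** If all d discordant pairs go one way, the two-sided p is 2 × 0.5^d.

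- d = 5: 2/32 = 0.0625, not significant.
- d = 6: 2/64 = 0.031, significant.
- With more discordant pairs the requirement is 7 of 7 (0.016), 8 of 8 (0.008; 7 of 8 fails), 8 of 9 (0.039) or 9 of 10 (0.021).
- At one-sided 0.05, five of five suffices: 1/32 = 0.031.

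Six is therefore a minimum that rests on the two-sided assumption. With nine or ten discordant pairs, one contrary pair is tolerated.

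**Step 2: exact power of the sign test, 10 pairs.** Let a = P(only the PAE man is continent) = p_PAE(1 − p_C), and b = P(only the control is continent) = p_C(1 − p_PAE). Power is the trinomial probability of all outcomes (i for, j against) that reject.

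- 40% v 80%: a = 0.8 × 0.6 = 0.48, b = 0.4 × 0.2 = 0.08, tied 0.44. The outcome (6,0) has probability 210 × 0.48^6 × 0.44^4 = 0.096. Adding (7,0) 0.060, (8,0) 0.0245, (8,1) 0.009, (9,0) 0.006, (9,1) 0.001 and (10,0) 0.0006 gives **0.197**.
- 50% v 80%: a = 0.40, b = 0.10, tied 0.50. The same sum gives **0.090**.
- One-sided 0.05: 0.34 and 0.19.
- With 8 complete pairs, two-sided: 0.09 and 0.04.
- Actual two-sided type I error with equal true rates of 80% to 50%: 0.002 to 0.009. The test is conservative, not invalid.

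**Step 3: the same effect analysed as a weight.** The shift on the latent scale is Φ⁻¹(p_PAE) − Φ⁻¹(p_C).

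- 40% v 80%: 0.842 + 0.253 = 1.095 SD. For the paired t-test the noncentrality is 1.095 × √10/√2 = 2.45 on 9 df, and power is 0.59. Signed-rank (simulated): 0.57.
- 50% v 80%: 0.842 SD, noncentrality 1.88, power 0.39. Signed-rank: 0.38.
- A within-pair correlation of 0.3 raises the paired t-test to 0.75 and 0.52.

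**Step 4: the unfavourable case for grams.** Suppose every continent man weighs exactly 0 g, so that weights vary only among men who leak.

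| Control v PAE continent | Sign test | Paired, continuous weights | Signed-rank, continent = 0 g |
|---|---|---|---|
| 40% v 80% | 0.20 | 0.57–0.59 | 0.34–0.35 |
| 50% v 80% | 0.09 | 0.38–0.39 | 0.17 |
| 80% v 95% | 0.004–0.006 | 0.35–0.36 | 0.006 |

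In the first two rows the gain shrinks but remains nearly twofold. In the last row, with 80% of controls at 0 g, it disappears.

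**Step 5: definitions that affect the comparison.**

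- A gain below 400 g is continence in 8.3 but mild incontinence in 9.5.2.8, so the binary outcome has no single definition.
- Section 9.5.2.8 lists a day-12 pad test. Section 5.6 (Visit 5) and the schedules in Appendices A1 and A2 do not; there, and in 5.7, the test starts at month 3.

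**The case against.** The strongest reply is that this is a proof-of-concept study with no formal sample size, that continence is one of fourteen listed objectives, and that return to continence is a clinical status which a proportion answers directly. That stands. It is a reason to keep the proportion and add a gram analysis beside it. It does not justify omitting the grams, and the transfusion precedent points the same way.

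Several stronger readings are tempting, but the documents do not support them.

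- *Most of the continence information is thrown away.* Section 9.1 summarises continuous variables in general and lists all CRF data, so the grams remain available. How much power is lost depends on continence rates and a weight distribution that the plan does not give.
- *Six one-way pairs is the plan's own threshold.* It follows only if the test is two-sided at 0.05, which is nowhere stated.
- *Two men leaking 20 g and 350 g necessarily fall in the same class.* They do under 8.3. Under 9.5.2.8 they differ if 20 g counts as insignificant.
- *Power is under 1% against 44%.* That contrast arises with the 400 g cut of 8.3 and assumed medians of 150 g and 50 g (log SD 1.2). It rests on one side of an unresolved contradiction.
- *A real effect will be reported as no difference.* No section says how a non-significant result will be worded.

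It is also fair to say that the gram analysis would still miss 41% to 62% of these large effects even under the favourable model (power 0.59 down to 0.38).

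**Conclusion.** The point holds as a matter of sensitivity. The plan measures leakage in grams, names only a binary comparison on at most ten pairs, and departs from its own handling of transfusion. At an assumed two-sided 0.05 the sign test has about 20% and 9% power for 40% v 80% and 50% v 80% continent. A paired analysis of the weights has about 58% and 39% if weights vary continuously, about 35% and 17% (signed-rank) if continent men weigh 0 g, and little or no advantage if about 80% or more of controls weigh 0 g. The rates, distribution and alpha are assumptions, so the size of the gain is a range. A reader might go further and infer that the sign test is wrong or that the endpoint should be replaced; neither follows. This is a cheap improvement to a secondary analysis.

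**What to change.** - In 9.5.2.8, following 9.5.2.3, add a paired comparison of 24-hour pad weight in grams at one pre-named visit, for example month 3. Use a signed-rank test, or a paired t-test on log(grams + 1), and report the within-pair difference with a 95% CI. State in advance how pairs with equal weights (such as both 0 g) and pairs with a missing weight are handled.
- Show grams descriptively at the other visits, and keep the proportion continent.
- State the alpha level and sidedness of the tests.
- Reconcile 8.3 with 9.5.2.8 on how a gain below 400 g is classed, and give a gram value for an insignificant increase if that term stays.
- Reconcile 9.5.2.8 with 5.6, 5.7 and Appendices A1 and A2 on whether the pad test is done at day 12.

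The cost is SAP and protocol wording; the gram analysis needs no new data or visits. The small downsides are one more secondary analysis and a result in grams that is less readable than a proportion, which is why the proportion stays in the table.
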